5.2.2.2 Adverse event collection and reporting

AE Collection

The following must be collected and documented on the appropriate eCRF by the Investigator:

- From signing the informed consent onwards through the Residual Effect period (REP), until the end of the REP all AEs (non-serious and serious), and AESIs.
- After the end of the REP until trial completion, all related SAEs and related AESIs.
- If in an individual patient only vital status information (Phase II patients only) is collected from a certain timepoint on, no further AEs or AESIs will be reported for this patient.

Trial Protocol Version 12

Page 67 of 241

Proprietary confidential information. © 2022 Boehringer Ingelheim International GmbH or one or more of its affiliated companies. All rights reserved.

[figure not shown]

Figure 5.2.2.2: 1 Adverse Event Collection and Reporting

The REP is defined as 42 days after the last trial medication application. All AEs which occurred through the treatment phase and throughout the REP will be considered as on treatment please see section 7.3.3. Events which occurred after the REP will be considered as post treatment events.

After the last per protocol contact the Investigator does not need to actively monitor patients for AEs. However, if the Investigator becomes aware of SAEs or AESIs that occurred after the last per protocol contact, the SAEs and AESIs should be reported by the Investigator to the Sponsor if considered relevant by the Investigator.

AE reporting to sponsor and timelines

The Investigator must report SAEs, AESIs, and non-serious AEs which are relevant for the reported SAE or AESI, on the BI SAE form immediately (within 24 hours) to the Sponsor's unique entry point (country specific reporting process will be provided in the ISF). In specific occasions the Investigator could inform the Sponsor upfront via telephone. This does not replace the requirement to complete and send the BI SAE form.

With receipt of any further information to these events, a follow-up SAE form has to be provided. For follow-up information the same rules and timeline apply as for initial information.

Information required

For each AE, the Investigator should provide the information requested on the appropriate (e)CRF pages and the BI SAE form, e.g. onset, end date, intensity, treatment required, outcome, seriousness, and action taken with the investigational drug(s). The Investigator should determine the causal relationship to the trial medication, the trial procedures outlined under section 6.2, and any possible interactions between the investigational drug(s) and a non-investigational product (NIMP)

The following should also be recorded as an (S)AE in the (e)CRF and SAE form (if applicable):

• Worsening of the underlying disease or of other pre-existing conditions

Page 68 of 241

Doc. No.: c02304008-15

Proprietary confidential information. © 2022 Boehringer Ingelheim International GmbH or one or more of its affiliated companies. All rights reserved.

• Changes in vital signs, ECG, physical examination and laboratory test results, if they are judged clinically relevant by the Investigator.

If such abnormalities already pre-exist prior trial inclusion they will be considered as baseline conditions.

All (S)AEs, including those persisting after trial completion must be followed up until they have resolved, have been sufficiently characterized, or no further information can be obtained.

Screening failures:

SAEs occurring in patients after having discontinued in the trial due to screening failures, i.e after the screening period and who did not receive any trial medication, are to be reported if the Investigator considered the SAE related to the screening procedure. SAE which occurred during the screening period are to be reported according to standard practices.

Pregnancy

In the rare case that a female partner of a subject participating in this clinical trial becomes pregnant, the Investigator must report immediately (within 24 hours) the drug exposure to female partners of male participants during pregnancy (DEDP) to the Sponsor's unique entry point (country- specific contact details will be provided in the ISF). The Pregnancy Monitoring Form for Clinical Trials (Part A) should be used.

The outcome of the pregnancy associated with the drug exposure during pregnancy must be followed up and reported to the Sponsor's unique entry point on the Pregnancy Monitoring Form for Clinical Trials (Part B).

As pregnancy itself is not to be reported as an AE, in the absence of an accompanying SAE, only the Pregnancy Monitoring Form for Clinical Trials and not the SAE form is to be completed. If there is an SAE associated with the pregnancy then the SAE has to be reported on the SAE form in addition.

The ISF will contain the Pregnancy Monitoring Form for Clinical Trials (Part A and B).

Exemption to (S)AE Reporting:

Disease Progression is a trial endpoint for analysis of efficacy and as such is exempted from reporting as an (S)AE. Progression of the patients underlying malignancy will be recorded on the appropriate pages of the (e)CRF as part of efficacy data collection only and will not be reported on the SAE Form. It will therefore not be entered in the safety database (ARISg) and hence not get expeditiously reported. Death due to disease progression is also to be recorded on the appropriate (e)CRF page and not on the SAE Form.

However, when there is evidence suggesting a causal relationship between the study drug(s) and the progression of the underlying malignancy, the event must be reported as an SAE on the SAE Form and on the (e)CRF.

Examples of exempted events of PD may be:

respective response criteria.

Doc. No.: c02304008-15 Trial Protocol Version 12 Page 69 of 241

Proprietary confidential information. © 2022 Boehringer Ingelheim International GmbH or one or more of its affiliated companies. All rights reserved.

• Progression of underlying malignancy (Progressive disease [PD]): if PD is clearly consistent with the suspected progression of the underlying malignancy as defined by the

- Hospitalization/Procedures due solely to the progression of underlying malignancy (PD)
- Clinical symptoms and/or signs of progression (without confirmation by objective criteria e.g. imaging, clinical measurement): if the symptom can exclusively be determined to be due to the progression of the underlying malignancy and does meet the expected pattern of progression for the disease under study.

Exempted events are collected and tracked following a protocol-specified monitoring plan.

Exempted events are monitored at appropriate intervals by the Data Monitoring Committee.

5.2.3 Dose Limiting Toxicity (DLT) definitions

DLTs will be assessed during the phase Ib escalation part of the study. The determination of the number of DLTs experienced during the first cycle of treatment will be used to identify the MTD of BI 836845 in combination with enzalutamide.

A study drug-related adverse event constitutes a DLT, if one of the following applies during treatment in the phase Ib escalation cohort:

- AST or ALT > 5x ULN (for baseline AST/ALT \leq ULN) or > (baseline value + 4x ULN) (for baseline AST/ALT > ULN)
- CTCAE Grade 3 or 4 toxicity (except for incompletely treated nausea, untreated vomiting, untreated diarrhoea, fatigue, infusion reaction, electrolyte, or AST/ALT).
- CTCAE Grade ≥2 infusion reaction despite adequate pre-medication.
- CTCAE Grade ≥2 nausea and/or vomiting persisting for 7 or more days despite antiemetic treatment.
- Any grade 4 hyperglycaemia (symptomatic or asymptomatic).
- Any Grade 3 hyperglycaemia lasting >48 hours.
- Any electrolyte grade 3 AE which is refractory to optimal correction therapy
- Seizure event of any CTCAE grade
- No recovery from a non-DLT CTCAE grade >2 toxicity to grade 1 within 14 days of administered dose
- Sustained fatigue/asthenia grade 3 for longer than 96 hours associated with deterioration of ECOG Performance Score
- Any other study drug related toxicity at any time point during the study considered significant enough to be qualified as DLT in the opinion of the investigators and confirmed by the safety review with the BI clinical monitor, will be reported as a DLT.

It is essential that patients are treated sufficiently according to supportive care standards.

As patients with a documented clinical benefit, e.g. objective tumour response or absence of tumour progression, will receive further treatment with the trial drug all DLT events in individual patients occurring at any time during treatment cycles, or the follow-up period, must be reported as an AESI.

BI Trial No.: 1280.8 Doc. No.: c02304008-15

Trial Protocol Version 12 Page 70 of 241

Proprietary confidential information. © 2022 Boehringer Ingelheim International GmbH or one or more of its affiliated companies. All rights reserved.

The decisions regarding dose escalation steps in the tolerability and safety phase will be made only upon review of the DLTs during the first cycle of treatment and after discussion between the sponsor and the clinical investigators at all sites, and in consideration of all the available toxicity, pharmacokinetic and pharmacodynamic data.

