4.1.3.3 Determination of the dose of BI 836845 in combination with enzalutamide

The phase Ib tolerability and safety phase (phase Ib escalation cohort) will be performed to determine the MTD, recommended phase II dose (RP2D) of BI 836845 in combination with enzalutamide using a 3+3 design in order to confirm the recommended dose to be used in the phase II randomised trial and exploratory expansion cohort.

Dosing with BI 836845 will be as follows:

- The starting dose of BI 836845 will be 750 mg (75%) total dose plus 160 mg (100%) daily dose of enzalutamide.
 - If 0 out of 3 patients experience a DLT enter 3 patients at highest dose of BI 836845
 - If 1 out of 3 patients experience a DLT enter 3 more patients at starting dose of BI 836845.
 - If 0 of 3 of these additional patients experience a DLT move to highest dose of BI 836845.
 - If ≥ 1 out of 3 of these additional patients experience a DLT trial is stopped.
 - o If ≥ 2 out of 3 patients experience a DLT trial is stopped.
- The highest dose of BI 836845 will be 1000 mg (100%) total dose plus 160 mg (100%) daily dose of enzalutamide.
 - o If \leq 1 out of 3 patients experience a DLT enter 3 additional patients at highest dose of BI 836845.
 - o If \geq 2 out of 3 patients experience a DLT:
 - If only 3 patients are entered at starting dose of BI 836845 enter additional 3 patients at starting dose of BI 836845
 - If 6 patients are already recruited in starting dose regimen recruitment into escalation part of trial is complete.

06 Jun 2022 **BI Trial No.: 1280.8**

Page 48 of 241

Trial Protocol Version 12 Proprietary confidential information. © 2022 Boehringer Ingelheim International GmbH or one or more of its affiliated companies. All rights reserved.

The MTD will be defined as the dose level at which one or less DLT is observed in six patients during the first cycle of treatment of each patient (28 days). See section 5.2.4

Non-evaluable patients for DLT will be replaced.

The decision on dose escalation and determination of next dose, the MTD, and/or recommended phase II dose (the exploratory expansion cohort will also use the same dose as Phase II) will be determined after discussion with the trial team comprising of at least one BI Clinical Monitor, BI project physician (TMM) and Coordinating Investigator, or designee, and taking into account patient safety.

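### The 48-hour limit on grade 3 hyperglycaemia in the DLT list has no effect, because the general grade 3/4 criterion already counts such events at any duration

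*Protocol*

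**What the plan says.** Protocol 5.2.3 sets the list up as a set of alternatives: "A study drug-related adverse event constitutes a DLT, if one of the following applies during treatment in the phase Ib escalation cohort". Three of the criteria matter here:

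- the general one: "CTCAE Grade 3 or 4 toxicity (except for incompletely treated nausea, untreated vomiting, untreated diarrhoea, fatigue, infusion reaction, electrolyte, or AST/ALT";
- grade 4 hyperglycaemia: "Any grade 4 hyperglycaemia (symptomatic or asymptomatic";
- grade 3 hyperglycaemia: "Any Grade 3 hyperglycaemia lasting >48 hours".

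The general criterion has no minimum duration, and hyperglycaemia is not among its exceptions. Fatigue is handled differently. It is excepted from the general criterion and then has its own time limit: "Sustained fatigue/asthenia grade 3 for longer than 96 hours associated with deterioration of ECOG Performance Score".

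On use of the count, 5.2.3 states: "The determination of the number of DLTs experienced during the first cycle of treatment will be used to identify the MTD". Protocol 4.1.3.3 turns the count into dose steps. At the starting dose, "If 0 out of 3 patients experience a DLT enter 3 patients at highest dose of BI 836845". One DLT in three leads to three more patients at that dose, and at the other end of the scale "2 out of 3 patients experience a DLT trial is stopped". Protocol 5.2.4 allows at most one DLT in six patients at the MTD. SAP 7.4.1 has no DLT definition of its own and refers to protocol 5.2.3.

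**The concern.** A criterion with a 48-hour threshold normally signals that shorter episodes are meant to be spared. Here nothing spares them, because the general criterion catches the same events first. Someone applying the list literally counts a 24-hour grade 3 episode. Someone who assumes that the 48-hour line must mean something does not.

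The DLT count is the primary endpoint of the escalation part. It sets the MTD and informs the dose carried into the expansion cohort and phase II. In the escalation part a DLT is also an adverse event of special interest (5.2.2.1), and DLTs are tabulated both for the first course and for all courses (7.3.3). Which reading was used therefore affects the safety tables as well as the dose decision. Section 1.2.1 names disturbed glucose homeostasis as a common toxicity of agents aimed at the IGF-1 receptor, so the event type is not far-fetched.

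**Working it through.** **The plan's own figure.** The MTD criterion in 5.2.4 is one in six, stated as 17%. 1/6 = 16.7%, which rounds to 17%, so the figure reproduces. No sample size or error rate depends on this point.

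**Step 1: apply each criterion to a drug-related grade 3 hyperglycaemia of 48 hours or less.**
- General grade 3/4 criterion: met. There is no duration limit and no exception.
- Grade 4 criterion: not met.
- 48-hour criterion: not met.
- Result under an any-one-suffices list: DLT.

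For a grade 3 episode longer than 48 hours, both the general and the 48-hour criteria are met, so it is again a DLT. The 48-hour criterion never changes a result.

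**Step 2: compare the other toxicities that have a narrower rule of their own.** AST/ALT, infusion reaction, nausea and vomiting, electrolytes and fatigue all appear in the exception list. Grade 3 hyperglycaemia has a narrower rule and does not. The electrolyte exception does not clearly cover it: Tables 5.2.5:1 and 5.2.5:2 list blood glucose under a separate heading from sodium and potassium.

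**Step 3: look for a resolution elsewhere.** Sections 4.1.3.3, 4.1.4.1 and 5.2.4 use the count without redefining it. The closing criterion in 5.2.3, which leaves other toxicities to judgement, can only add DLTs. SAP 7.4.1 points back to 5.2.3.

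**Step 4: carry both readings through 4.1.3.3 and 5.2.4.** A short episode here means drug-related grade 3 hyperglycaemia of 48 hours or less in cycle 1.

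| Cohort | Other DLTs | Short episodes | If not counted | If counted |
|---|---|---|---|---|
| Starting dose, 3 patients | 0 | 1 | 0/3: escalate | 1/3: add 3 at same dose |
| Starting dose, 3 patients | 0 | 2 | 0/3: escalate | 2/3: trial stopped |
| Starting dose, 6 patients (other DLT in first 3, episode in second 3) | 1 | 1 | 1/6: move to highest dose | 2/6: trial stopped |
| Highest dose, 3 patients | 0 | 1 | 0/3: add 3 | 1/3: add 3 (same step) |
| Highest dose, 6 patients | 1 | 1 | 1/6: MTD criterion met | 2/6: not met |

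**Step 5: how often?** The documents do not say. Section 1.2.1 reports one transient grade 3 case among 81 patients on monotherapy, 1/81 = 1.2%, with no duration in hours.

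**The case against.** The strongest reply is that a list of alternatives gives one definite answer: the event counts. Failing the 48-hour criterion does not clear an event that meets another one. This stands. A reader might infer that the two criteria classify the same patient in opposite ways, but the text does not support that. No criterion says that an episode under 48 hours is not a DLT. The defect is an idle criterion whose apparent purpose conflicts with the literal rule.

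The exception list is also less tidy than the comparison in Step 2 suggests. Diarrhoea is excepted without a rule of its own, seizure has its own rule without being excepted, and the grade 4 hyperglycaemia line is redundant too. So the pattern suggests an oversight but does not prove one. Those cases do differ, though. The seizure rule widens the general criterion and the grade 4 line agrees with it. The 48-hour line carries a limit that never operates.

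A reader might also infer that any single extra DLT in three changes the next step. That is true at the starting dose only. At the highest dose 0/3 and 1/3 lead to the same step.

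A reader might put a probability on the problem: 1 - (80/81)^6 = 0.072 for at least one case in six patients. That figure is not an estimate of the disputed event. It uses a monotherapy count, and neither the duration nor the cycle is given. Section 1.2.1 itself calls such events relatively infrequent, and higher rates on the combination would be assumption alone.

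Finally, dose decisions are discussed between sponsor and investigators with all toxicity data in view (5.2.3). The SAP introduction says that the escalation part has already been analysed and reported. Both are correct. Discussion does not settle which events enter the count, but rewording the protocol now cannot alter a dose already chosen.

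**Conclusion.** The point holds as a drafting defect in the definition behind the escalation part's primary endpoint. Read literally, every drug-related grade 3 hyperglycaemia is a DLT and the 48-hour criterion is idle. Giving that criterion meaning requires an exception that the text does not contain.

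The scope is narrow: drug-related grade 3 episodes of 48 hours or less in phase Ib escalation, and only those in cycle 1 for the MTD count. Grade 4 episodes and longer grade 3 episodes count under either reading. Within that scope, one or two events can change the step taken at the starting dose, and one event can decide whether the MTD criterion is met in a cohort of six. These results follow from the written rules and need no assumed rate. How likely such an event was cannot be judged from the documents, and nothing in them shows that any actual dose decision was affected.

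**What to change.** Reconcile the general criterion and the hyperglycaemia criteria in protocol 5.2.3 so that a single rule governs grade 3 hyperglycaemia. Which rule is right is for the sponsor's safety team. This is a change of one line. No separate SAP wording is needed, because SAP 7.4.1 takes its definition from protocol 5.2.3.

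Because the escalation data are already analysed, add a short statement to the DLT tables and listing:

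- which reading was applied;
- whether any escalation patient had a drug-related grade 3 hyperglycaemia of 48 hours or less;
- whether that patient's DLT status, the MTD or the recommended phase II dose would differ under the other reading.

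The check covers a part planned for about 9 to 12 patients, so the work is small. Fasting glucose is scheduled only at screening and on Day 1 of each cycle, with EOT added in the flow chart, so durations may have to come from adverse event dates or unscheduled samples. If a duration cannot be established, say so.

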5.2.4 Maximum Tolerated Dose (MTD) and Recommended Phase II Dose (RP2D)

The maximum tolerated dose in this study is defined as the highest protocol dose level of BI 836845 in combination with enzalutamide, at which no more than 1 out of 6 patients in a cohort experiences a drug related DLT during the first 28 day treatment cycle – i.e. the incidence of a dose limiting toxicity is no more than 17%. DLT events experienced after the start of the second treatment course will be examined separately.

The MTD or a lower dose level will be chosen as the recommended phase II dose (RP2D) based on the totality of the safety data available at the time that 6 evaluable patients have finished course 1 of treatment at the MTD (or RP2D if MTD not reached); at the earliest. The discussion and agreement on dose selection between the phase Ib escalation investigators and the sponsor will be documented and communicated to all participating sites. The recommended phase II dose (RP2D) will also be used for the phase Ib expansion cohort.

5.2.5 Assessment of safety laboratory parameters

Safety assessments, including clinical and laboratory evaluations will be assessed during treatment cycles according to Flow Chart. Adverse events are to be graded according to the National Cancer Institute (NCI) Common Terminology Criteria for Adverse Events, CTCAE version 4.03, 14 June 2010 (R10-4848). Changes in laboratory tests from baseline will be assessed.

Assessment of safety laboratory parameters prior to approval of protocol version 10

Blood samples, including fasting serum samples (fasting state from midnight the night before), will be collected up to one day prior to the scheduled time points as specified in the Flow Chart and analysed in a laboratory facility at (or close to) the investigational site. Safety laboratory examinations include hematology, biochemistry, coagulation and urine examination. See Table 5.2.5: 1 for details. Futher samples may be taken throughout the course of the study when deemed appropriate by the investigator. All analyses are to be performed by the local clinical laboratory.

Table 5.2.5: 1 Safety Laboratory Parameters to be performed prior to approval of protocol version 10

Category	Test Name
Haematology:	Red blood cell count (RBC), haemoglobin, white blood cell count (WBC), reticulocytes and differential, platelets
Biochemistry:	Sodium, potassium, calcium, magnesium, creatinine, aspartate amino transferase (AST), alanine amino transferase (ALT), alkaline phosphatase, lactate dehydrogenase, total bilirubin, urea, uric acid, creatine phosphokinase (CPK). In case of pathological CPK further evaluation (e.g., by Troponin assays, CK-MM, CKMB, ECG exam)

BI Trial No.: 1280.8 Doc. No.: c02304008-15

Trial Protocol Version 12 Proprietary confidential information. © 2022 Boehringer Ingelheim International GmbH or one or more of its affiliated companies. All rights reserved.

Page 71 of 241

Table 5.2.5: 1 Safety Laboratory Parameters to be performed prior to approval of protocol version 10 (continued)

Category	Test Name
	should be performed and the findings documented. GFR will be estimated by the Cockgroft-Gault formula utilizing serum creatinine values and recorded in the eCRF.
Coagulation parameters	Prothrombin time (PT), international normalised ratio (INR) where therapeutically indicated and activated partial thromboplastin time (aPTT).
Urine examination:	pH, glucose, erythrocytes, leukocytes, protein, nitrite will be analyzed by dipstick (semi-quantitative measurements: -, +, ++, ++++, ++++). In case of abnormal findings, further evaluation should be performed and the findings documented.
Other – fasting (only at screening and Day 1 of every cycle)	Blood glucose and HbA1C

Assessment of safety laboratory parameters after approval of Protocol version 10

Blood samples will be collected up to one day prior to the scheduled time points as specified in the Flow Chart and analysed in a laboratory facility at (or close to) the investigational site. Safety laboratory examinations include hematology, biochemistry and electrolytes. See Table 5.2.5: 2 for details. Futher samples may be taken throughout the course of the study when deemed appropriate by the investigator. All analyses are to be performed by the local clinical laboratory.

Table 5.2.5: 2 Safety Laboratory Parameters to be performed after approval of protocol version 10

Category	Test Name
Haematology:	haemoglobin, white blood cell count (WBC), platelets
Biochemistry:	Sodium, potassium, creatinine, aspartate amino transferase (AST), alanine amino transferase (ALT), lactate dehydrogenase, total bilirubin
Other	Blood glucose*

^{*} Glucose may be obtained non-fasting, but in case elevated should be repeated fasting. If Glucose is repeated fasting, only the fasting value should be captured in the eCRF.

Doc. No.: c02304008-15 Trial Protocol Version 12 Page 72 of 241

Proprietary confidential information. © 2022 Boehringer Ingelheim International GmbH or one or more of its affiliated companies. All rights reserved.

If blood sampling at the trial site is not possible, safety lab analyses can be performed at a local lab. The results of the lab tests must be transferred to the investigator who ensures medical review and proper documentation in the eCRF.

